POD	Post-Operative Day counting the day of surgery as POD0
PPC	Postoperative Pulmonary Complication
PRIME-AIR	Mnemonic name for the study
PROMIS	Patient-Reported Outcomes Measurements
SAP	Statistical Analysis Plan
SDCC	Statistics and Data Coordinating Center
UC	Usual Care
WBC	White Blood Cell count

4 Overview

4.1 Study Design

The PRIME-AIR trial is a prospective multicenter randomized controlled pragmatic trial with a blinded assessor. We studied 751 adult participants with moderate or high risk for PPCs undergoing elective major open abdominal surgery. Enrolled participants were randomized 1:1 to receive either the perioperative intervention (PRIME-AIR bundle) or control (usual care); randomization was stratified by site.

The overall aim for this specific analysis is to compare the number and severity of PPCs in patients receiving an individualized perioperative anesthesia-centered bundle to those receiving usual anesthetic care during open abdominal surgery as well as the secondary outcomes for the comparison between the two treatment groups.

4.2 Description of Intervention

Our intervention is an anesthesia centered individualized bundle consisting of pre-, intra-, and postoperative interventions aimed at optimizing perioperative lung expansion. The bundle consists of the following perioperative interventions:

[Type here]

1. preoperative education on postoperative pulmonary complications
2. individualized PEEP with recruitment maneuvers to maximize respiratory system compliance (C_{rs}) and minimize driving pressures (DP)
3. protocolized neuromuscular blockade administration and reversal based on neuromuscular monitoring
4. postoperative incentive spirometry with daily goals and adherence enhanced by supervision and
5. encouragement for ambulation with daily goals.

4.3 Description of Control Group (Usual Care)

The control group follows the usual care at each of the individual sites, without any attempt to standardize the care provided across the institutions. As all sites are academic medical centers or affiliated with academic medical centers, the usual care arm is expected to be representative of current high-quality care for the population.

4.4 Inclusion-Exclusion Criteria and General Study Population

4.4.1 Participant Inclusion Criteria

All the following inclusion criteria (copied from "Inclusion criteria" from Section III of the protocol) must be met for a participant for the study:

- Adults (≥ 18 years) scheduled for elective surgery with expected duration ≥ 2 hours
- Open abdominal surgery including: gastric, biliary, pancreatic, hepatic, major bowel, ovarian, renal tract, bladder, prostatic, radical hysterectomy, and pelvic exenteration
- Intermediate or high risk of PPCs defined by an ARISCAT risk score ≥ 26 (Appendix 1 of this document)

Potential individuals excluded for failure to meet these inclusion criteria are not recorded in the study database.

4.4.2 Participant Exclusion Criteria

Any of the following (copied from "Exclusion criteria" from Section III of the protocol) would preclude an individual from participating in the study:

- Inability or refusal to provide consent

- Inability or significant difficulty to perform any study interventions, including incentive spirometry, ambulation and/or maintaining follow-up contact with study personnel for up to 90 days after the date of surgery
- Participation in any interventional research study within 30 days of the time of the study
- Previous surgery within 30 days prior to this study
- Pregnancy
- Emergency surgery
- Severe obesity (above Class I, $\text{BMI} \geq 35 \text{ kg/m}^2$)
- Significant lung disease: any diagnosed or treated respiratory condition that (a) requires home oxygen therapy or non-invasive ventilation (except nocturnal treatment of sleep apnea without supplemental oxygen), (b) severely limits exercise tolerance to <4 METs (e.g., patients unable to do light housework, walk flat at 4 miles/h or climb one flight of stairs), (c) required previous lung surgery, or (d) includes presence of severe pulmonary emphysema or bullae
- Significant heart disease: cardiac conditions that limit exercise tolerance to <4 METs
- Renal failure: peritoneal or hemodialysis requirement or preoperative creatinine $\geq 2 \text{ mg/dL}$
- Neuromuscular disease that impairs ability to ventilate without assistance
- Severe chronic liver disease (Child-Turcotte-Pugh Score >9, Appendix 3)
- Sepsis
- Malignancy or other irreversible condition for which 6-month mortality is estimated $\geq 20\%$
- Bone marrow transplant
- Pulmonary hypertension

4.5 Outcome Measures

The protocol ("Study Outcomes" in Section V of the protocol) lists the outcomes. For convenience they are separated into efficacy and safety outcomes in the list below.

4.5.1 Efficacy Outcomes

- The primary outcome is the participant's PPC severity during the first 7 days after surgery. PPC severity will be classified from none to Grade 4 based on the most

[Type here]

serious PPC occurring during those 7 days. The protocol provides details of the specific PPCs in Table 5; this is included in Appendix 2 for reference.

- Secondary efficacy outcomes include:
 - Proportion of participants with highest grade being Grade 1 or 2 through POD 7
 - Proportion of participants with highest grade being Grade 3 or 4 through POD 7, 30, 90 (3 outcomes)
 - Proportion of participants with Hypoxemia by POD 7 (either Grade 1 or Grade 2)
 - Proportion of participants with Atelectasis by POD 7
 - Proportion of participants with Pneumonia (suspected and proved) by POD 7
 - Proportion of participants with Ventilatory dependence or failure by POD 7

4.5.2 Safety Outcomes

The co-primary safety outcomes will be: 1) the proportion of patients with any intraoperative cardiovascular events or pneumothorax; and 2) the proportion with both intraoperative hypoxemia and rescue recruitment maneuvers. Specifically:

- Proportion of participants with intraoperative cardiovascular events (hypotension, bradycardia, tachycardia, arrhythmias, new ST-segment changes, and cardiac arrest) or pneumothorax
- Proportion of participants with both intraoperative hypoxemia and rescue recruitment maneuvers

Other secondary safety outcomes include:

- Length of postoperative oxygen therapy/other respiratory support
- Length of hospital stay
- Proportion of participants with any major extrapulmonary complications (detailed definition is in Appendix I of the protocol; included in Appendix 3 of this document for reference)

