Managing anesthesiologists will be those usually composing the team caring for abdominal surgery patients at the participating sites. Anesthesiologists will be randomized into two groups, caring only for either controls or interventional patients, to minimize contamination, i.e., avoid anesthesiologists being exposed to the bundle and then treating control patients. The site PI or study coordinator will be available in the operating room to monitor and provide support with the interventions. This phase will consist of two components (Fig. 1):

A. PEEP and Lung Recruitment - Mechanical Ventilation with Individualized PEEP:

Perioperative lung expansion will be accomplished by PEEP individualization through maximization of the patient's respiratory system compliance (C_{RS}). This corresponds to the minimization of driving pressures, i.e., the difference between plateau pressure and PEEP during mechanical ventilation. This **maximal compliance strategy** will be started immediately after induction and repeated at least hourly throughout the surgery (see Appendix III for additional details).

PEEP individualization will be determined by a recruitment maneuver followed by a decremental PEEP titration (Fig. 3). The stepwise **recruitment maneuver** will consist of the increase of PEEP from 5 to 20 cmH₂O in 5 cmH₂O steps of 30-sec each, as long as the patient's plateau pressure (P_{plat}) =30-32 cmH₂O (PEEP can be increased by 2-3 cmH₂O instead of by 5 cmH₂O to achieve P_{plat} =30-32 cmH₂O). Starting at this maximally achieved PEEP, PEEP will be decreased in 3 cmH₂O steps of 45-75 sec until a maximum C_{RS} is identified by a reduction in C_{RS} at a lower PEEP following a larger C_{RS} at a higher PEEP (Fig. 3). The minimum PEEP along the decremental steps will be 2 cmH₂O. Once the PEEP for maximal C_{RS} is identified, the largest PEEP level achieved during the recruitment maneuver will be used for 30-sec (in order to reinforce lung recruitment), followed by setting PEEP as the value that maximized C_{RS} . The procedure will be repeated on an hourly basis, and following any significant event producing a $\geq 15\%$ reduction in C_{RS} (e.g., significant change in surgical table position, application of surgical retractors, endotracheal tube disconnection, endotracheal tube suction). Similar adjustments will be performed in

[figure not shown]

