Fig. 3. Decremental PEEP titration protocol following a stepwise recruitment maneuver. Respiratory system compliance (C_{RS}) is measured at each step (●) and the PEEP corresponding to the maximum compliance is set as the individualized PEEP. In this example, titration would be stopped at 8 cmH₂O and the final PEEP set at 11 cmH₂O.

case of $\square 15\% C_{RS}$ increases (i.e. removal of retractors) in order to avoid overinflation if triggers of lung derecruitment are removed.

Other mechanical ventilation settings will be: volume controlled ventilation, tidal volume (V_T)=6-8mL/kg of predicted body weight, F_iO_2 titrated for the target $SpO_2 \geq 96\%$ (F_iO_2 increased only to maintain that target while avoiding hyperoxia), I:E ratio 1:2 and respiratory rate aiming at normocapnia ($P_{ET}CO_2=32-42$ mmHg and/or $P_aCO_2=35-45$ mmHg, if available).

B. Muscle relaxant optimization – Individualized Administration and Reversal of Neuromuscular Blocking Agents:

Only intermediate-acting neuromuscular blocking agents will be used (Table 2). Induction doses of muscle relaxants will be routine: Cisatracurium (≤ 0.2 mg/kg), rocuronium (≤ 1.2 mg/kg), vecuronium (≤ 0.1 mg/kg). Given the difficulty of precise dosing due to the presentation of the medications, doses 25% higher (or to the next round mL, e.g., 10 mg for rocuronium, 2 mg for cisatracurium, 1 mg for vecuronium with usual presentations) will be considered as consistent with the intent of the protocol. Succinylcholine can be used and dosed at the anesthesia team's discretion. Maintenance doses will be administered as required by surgical conditions and following confirmation of the presence of twitches in the train-of-four (TOF) stimulation.

Readministration of muscle relaxants will be avoided as possible when <2 twitches are present unless specific clinical conditions such as diaphragmatic contraction indicate otherwise. Maintenance doses will be limited to (Table 2): Cisatracurium (≤ 0.03 mg/kg), rocuronium (≤ 0.2 mg/kg) and vecuronium (≤ 0.015 mg/kg). As described for the induction dose, we will consider doses $\leq 25\%$ higher than the target dose or to the next round dose in milliliters as consistent with the intent of the protocol.

Table 2. Maximal intubating and maintenance doses of muscle relaxants to be used during the PRIME-AIR trial.

	Dose (mg/kg)	
	Intubation	Maintenance
Cisatracurium	0.2	0.03
Rocuronium	1.2	0.2
Vecuronium	0.1	0.015

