Postoperative Mechanical Ventilation (if applicable): The pre- or intraoperative decision to transfer a patient to the critical care unit will be made by clinical staff and recorded. To maintain the basic tenet of a recruited lung into the postoperative period, patients requiring mechanical ventilation postoperatively will receive at least one PEEP titration maneuver per day as described above and in keeping with interventions utilized in ICU patients⁴⁵. This is consistent with the evidence on the beneficial effect of low driving pressures to outcomes of surgical^{8,46} and ICU patients⁴⁷. Of note, recruitment maneuvers and PEEP levels in our protocol are substantially different from those utilized in the ART trial and lead to values comparable to the control lower-mortality arm of that trial⁴⁸. We will monitor if the PEEP optimization maneuver and the resulting PEEP used at least once a day. In general, this or alternative methods based on principles of lung expansion should be attempted if considered feasible by the ICU clinical team. Mechanical ventilation in the ICU will be done at the discretion of the critical care team. Recruitment maneuvers and PEEP titration are part of the usual care of mechanically ventilated ICU patients, and not expected to constitute a significant challenge to care providers.

Study Protocol for the Control Group:

The control group will consist of a *usual care* group, managed in a manner consistent with routine perioperative medical practice at the participating hospitals and of the attending anesthesiologists. This will increase the pragmatic character of the trial, as well as generalizability of our results. This design improves safety monitoring by providing an ability to detect harmful effects relative to usual care. It also strengthens the findings of the trial by emphasizing their pragmatic meaning. Details of usual care in participating sites are described in Table 4. This survey of practices in our 14 participating sites indicated that usual care corresponded to minimal individualization of intraoperative PEEP, infrequent use of any systematic management of neuromuscular blockade, unusual enforcement of incentive spirometry and rare preoperative education.

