- I. **Hemodynamic instability:** The recruitment maneuver and PEEP adjustment will be interrupted if the patient becomes bradycardic or tachycardic, develops a new arrhythmia, or becomes severely hypotensive (systolic blood pressure < 80 mmHg or mean blood pressure <50 mmHg). The patient will be managed by the primary anesthesia team if any hemodynamic changes occur during the recruitment maneuver or decremental PEEP titration. PEEP levels will be decreased for any urgent clinical reasons at the discretion of the managing anesthesia team. In the absence of an emergency need for change, the

anesthesia team caring for the patient will consider addressing any reasons of hemodynamic changes with intravenous fluids, vasoactive medications, and/or a stepwise adjustment of PEEP consisting of reducing PEEP by 2-5 cmH₂O. The anesthesia team will reassess repeating the recruitment maneuvers and PEEP optimization once the patient is stable (heart rate <100 beats/minute, SBP>100 mmHg). Anesthesiologists are experienced at reducing or responding to these events during usual care for surgery.

- II. Respiratory deterioration:** It is at the primary anesthesiologist's discretion to change the protocol ventilator settings if any emergent respiratory deterioration is observed. In the absence of an emergency need for change, a new PEEP optimization will be performed. If it fails to improve SpO₂, FiO₂ will be increased by 0.1-0.2 until a SpO₂≥96% is obtained. If plateau pressures are beyond 30 cmH₂O, we will follow the guidelines provided by the ARDSnet to maintain plateau pressures below this threshold¹⁷: if P_{plat} >30 cmH₂O: decrease V_T by 1mL/kg PBW steps (minimum = 4 mL/kg PBW); if later P_{plat} <25 cmH₂O and V_T <6 mL/kg PBW, increase V_T by 1 mL/kg PBW until P_{plat} >25 cmH₂O or V_T=6 mL/kg PBW; if P_{plat} <30 cmH₂O and breath stacking or dyssynchrony occurs, V_T may be increased in 1mL/kg PBW increments to 7 or 8 mL/kg PBW as long as P_{plat} remains ≤30 cmH₂O.

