***Targeted AEs:**

Acute myocardial ischemia or infarction
Cardiogenic pulmonary edema
Arrhythmia
Cardiac arrest
Stroke
GI bleeding
Anastomotic Breakdown
Paralytic ileus
Acute liver failure
Acute renal failure
Systemic inflammatory response syndrome
Surgical site infection
Urinary tract infection
Bacteremia
Sepsis
Septic shock
Infection - source uncertain
Disseminated intravascular coagulation
Postoperative hemorrhage
Thromboembolism
Pulmonary embolism
ARDS

AEs with Expedited Reporting: Only a subset of SAEs will have expedited reporting to the SIRB and the DSMB. We propose that only the following categories of events have expedited reporting (within 7 days of receipt by the SDCC):

- Any unanticipated problem (defined in the Detailed Protocol);
- Any AE that is serious, unexpected and suspected of being related (probably or possibly related) to the study procedures;
- Any occurrence of hemodynamic or respiratory instability, or pneumothorax, occurring during surgery and potentially arising from participation in the study.
- All adverse events that are serious, unexpected and occurring intraoperatively and immediately postoperatively (Day 0-1).

Definition of severe intraoperative respiratory AEs and hemodynamic instability. We define the intraoperative adverse events related to severe respiratory events (severe hypoxemia, pneumothorax) or severe hemodynamic instability as follows:

- Severe hypoxemia: SpO₂ ≤92% or 2% below the participant's preoperative room air value (if that value is ≤92%) for at least 10 minutes; OR increase in FiO₂ to 1.0 preceded by a SpO₂ ≤95% in the previous 5 minutes (excluding in preparation for extubation); AND requiring treatment in intensity or duration

beyond the usual intraoperative requirements according to the participant's anesthesiologist.

- Pneumothorax: presence of air in the pleural cavity occurring during surgery and requiring intervention
- Hemodynamic instability: SBP>160 or <80 mmHg, MAP>120 or <50 mmHg, HR>140 or <50 bpm, or deviations by more than 20% in any of those parameters from patient's baseline for >3 minutes despite treatment or cardiac events (e.g. significant arrhythmias, ST segment changes or cardiac arrest); AND requiring treatment in intensity or duration beyond the usual intraoperative requirements according to the participant's anesthesiologist

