5.3 Intraoperative Characteristics

A range of intraoperative characteristics will be used to describe the surgical course of the two groups, and the impact of the intervention bundle on intraoperative characteristics. These include:

- duration of surgery
- duration of mechanical ventilation
- multiple measures of the mechanical ventilation itself (e.g, tidal volume, PEEP, peak pressure, modified driving pressure (based on PEEP) and modified respiratory system compliance, etc.)
- heart rate
- mean arterial pressure
- fluids (crystalloids; colloids)
- blood loss
- vasoactive medications

6 General Analysis Considerations

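### The second co-primary safety outcome counts intraoperative hypoxemia only when a rescue recruitment maneuver was also given, and the SAP sets no hypoxemia-only comparison beside it

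*SAP*

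**What the plan says.** **The outcome.** SAP 4.5.2 lists two co-primary safety outcomes. The second is "the proportion with both intraoperative hypoxemia and rescue recruitment maneuvers". The protocol (section V, Secondary Outcomes) has the same joint event as a secondary outcome. Under SAP 8.2 and 6.1.4 it gets a Cochran-Mantel-Haenszel (CMH) test stratified by site, and a relative risk with 95% confidence limits.

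**Response to deterioration, bundle arm.** Protocol VII, Protections Against Risk, item II, concerns the protocol's ventilator settings: "In the absence of an emergency need for change, a new PEEP optimization will be performed". FiO2 is raised if that fails. Protocol V, Intraoperative Phase, part A, says what an optimization involves: "PEEP individualization will be determined by a recruitment maneuver followed by a decremental PEEP titration".

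**Response to deterioration, control arm.** Controls are "managed in a manner consistent with routine perioperative medical practice at the participating hospitals" (Protocol V, Study Protocol for the Control Group). SAP 4.3 adds that this is "without any attempt to standardize the care provided across the institutions". Anesthesiologists are randomized too, and only those delivering the bundle are trained in it (Protocol IV, Randomization).

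**Hypoxemia elsewhere.**
- Protocol V, Secondary Outcomes, calls intraoperative hypoxemia an event that needs quantifying.
- Protocol Appendix I lists it among intraoperative adverse events with no rescue condition.
- Protocol VI plans a between-arm comparison of lung mechanics and gas exchange.
- Protocol IX defines severe intraoperative hypoxemia as an adverse event.
- In the SAP, the only separate hypoxemia outcome is the postoperative one through day 7 (4.5.1). SAP 5.3 opens with "A range of intraoperative characteristics will be used to describe the surgical course of the two groups" and names no SpO2 or hypoxemia measure.

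**The concern.** A between-arm safety outcome should count events by a rule that does not depend on how each arm is managed. Here a hypoxemic patient is counted only if the clinician also gave a particular treatment. The protocol makes that treatment the first step in one arm and leaves it to local habit in the other. The scoring rule is the same in both arms, but the chance of meeting its second half need not be.

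A reader of the primary paper would see a co-primary safety ratio and could not tell more hypoxemia from more maneuvers. A ratio above 1 could accompany a bundle that reduces hypoxemia, and a ratio below 1 could accompany one that increases it. The first co-primary outcome does not share this feature: its cardiovascular events and pneumothorax are listed with no rescue condition.

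**Working it through.** The documents state no rate, effect size or power for this outcome, so there is no planned figure to reproduce. The only documentary input below is the planned 375 per arm (SAP 4.6). All rates are assumptions.

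**Identity.** Let h be the probability of intraoperative hypoxemia and r the probability of a counted maneuver given hypoxemia, with subscript I for the bundle and C for usual care. Then

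RR(composite) = (h_I × r_I) / (h_C × r_C) = (h_I / h_C) × (r_I / r_C).

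A hypoxemia-only comparison reports the first factor. The composite reports the product.

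**Equal hypoxemia.** With h_I = h_C, RR = r_I / r_C:

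| | r_C = 0.2 | r_C = 0.5 | r_C = 0.8 |
|---|---|---|---|
| r_I = 0.5 | 2.5 | 1.0 | 0.63 |
| r_I = 0.7 | 3.5 | 1.4 | 0.88 |
| r_I = 0.9 | 4.5 | 1.8 | 1.13 |

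For example, with h = 10% in both arms and r of 80% versus 40%, the risks are 8% and 4%, so RR = 2.0 (approximate 95% limits 1.09 to 3.66 at 375 per arm).

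**Chance of P<0.05 with equal hypoxemia.** Two-sided two-proportion normal approximation, unstratified, 375 per arm, r_I = 0.7:

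| h in both arms | r_C = 0.2 | r_C = 0.5 | r_C = 0.8 |
|---|---|---|---|
| 2% | 30% | 8% | 6% |
| 5% | 64% | 13% | 6% |
| 10% | 91% | 21% | 8% |
| 20% | 100% | 39% | 12% |

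At h = 10% the expected counts are 375 × 0.07 ≈ 26 in the bundle arm, against 375 × 0.02 ≈ 8, 375 × 0.05 ≈ 19 and 375 × 0.08 = 30 in controls. The distortion is small when hypoxemia is rare or maneuver use is similar.

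**When hypoxemia really differs.**
- *Bundle halves hypoxemia* (5% vs 10%, true ratio 0.5). With r of 0.7 vs 0.2 the risks are 3.5% and 2.0%, RR 1.75. With 0.8 vs 0.4 they are 4% and 4%, RR 1.0. With 0.7 vs 0.5 they are 3.5% and 5.0%, RR 0.7.
- *Bundle raises hypoxemia* (15% vs 10%, true ratio 1.5). With r of 0.2 vs 0.4 the risks are 3% and 4%, RR 0.75.
- *Bundle doubles hypoxemia, and protocol-triggered maneuvers are mostly not counted as rescue* (10% vs 5%, r_I = 0.1). The bundle risk is 1.0%; the control risk is 1.0%, 2.5% or 4.0% for r_C of 0.2, 0.5 or 0.8. RR is 1.0, 0.4 or 0.25, against a true ratio of 2.

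**Why r may differ by arm, and why its direction is open.** Item II of Protections Against Risk makes a recruitment-based optimization the first non-emergency step under protocol ventilation. The rule is not absolute. FiO2 may be "increased only to maintain that target while avoiding hyperoxia" (Protocol V, ventilation settings), PEEP may be altered at the anesthesiologist's discretion, and the clinical team may step in at any time. Controls may also receive maneuvers, which Protocol VII treats as part of standard care. Neither document says whether an optimization done for hypoxemia counts as rescue. If it counts, r_I is probably pushed up; if only out-of-protocol maneuvers count, r_I could be pushed down.

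**The case against.** **A hypoxemia comparison is arguably planned.** The protocol lists intraoperative hypoxemia in Appendix I, says it should be quantified, and plans a gas-exchange comparison. The list in SAP 5.3 is open-ended, SAP 7.5 tests those characteristics between arms, and the SAP covers one specific analysis. This stands in part: a reader might infer that no hypoxemia-only comparison exists anywhere in the plan, and the documents do not support that. What can be said is that the SAP specifies none beside the composite.

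**The mechanism is inferred.** The protocol speaks of optimization, not rescue. Hypoxemia is not among the routine triggers in Appendix III, and the usual-care survey (Table 4) covers individualized PEEP, not rescue maneuvers. This also stands. A reader might infer that the outcome is biased against the bundle, or by a known amount, but the documents give neither size nor direction. The tables show what is possible, not what is likely.

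**Safety oversight does not rest on this ratio.** Severe intraoperative hypoxemia is a reportable adverse event, the DSMB was told of significant intraoperative complications (SAP 4.7.3), and out-of-protocol setting changes made to hold SpO2 are recorded (Appendix III). That is correct and limits the consequence, but none of these is a specified between-arm comparison.

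**Requiring a rescue screens out trivial desaturation.** A fixed SpO2 threshold does this with less dependence on treatment, though not none: the duration of a desaturation and FiO2 practice also reflect management.

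**Conclusion.** The point holds as one of interpretation. As specified, the composite's relative risk mixes hypoxemia with clinician response, the protocol directs that response in one arm only, and the SAP gives the reader no hypoxemia-only result to separate the two. The size could be nil (equal counted maneuver use) or several-fold, and the sign can reverse in either direction. All of that rests on assumed rates and on an undefined rescue rule.

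A reader might infer that the trial's safety conclusion is formally invalid. The documents do not support that. No alpha, margin or decision rule is tied to this outcome, and SAP 6.6 says the confidence limits are not for hypothesis testing and treats secondary P-values as summaries if the primary endpoint is not significant. This is a cheap improvement to how a safety result is presented, with medium confidence that it matters in practice.

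**What to change.** Keep the composite and amend the SAP as follows.

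1. State whether protocol-triggered maneuvers count as rescue, with the same rule in both arms.
2. Add one row to SAP 4.5.2: intraoperative hypoxemia alone, one SpO2 criterion in both arms, CMH stratified by site with relative risk and 95% limits, labelled as specified after enrolment. A candidate is the SpO2 part of the severe-hypoxemia definition in Protocol IX: at or below 92%, or "2% below the participant's preoperative room air value" where that value is itself at or below 92%, for at least 10 minutes. Leave out its FiO2-to-1.0 and treatment-beyond-usual elements, which depend more directly on management.
3. Report maneuvers given for hypoxemia descriptively by arm, separately from scheduled ones.
4. State that no between-arm safety conclusion will be drawn from the composite alone, and that SpO2 duration and FiO2 practice remain partly management-dependent.

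The cost is one table row, a descriptive line and a few sentences, with no change to conduct and no outcome removed. There are two downsides. The row is specified late, since SAP 4.1 describes the 751 participants as already studied. And if hypoxemia was captured only jointly with the maneuver, the row cannot be produced and that should be stated as a limitation.
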